5.2 SUBJECT DE-IDENTIFICATION

Each subject will be identified with a unique number. All forms and documents related to each subject will be labeled with this unique number. At no time shall study paperwork or specimens be marked with a subject's name, any traceable identifier, or Protected Health Information (PHI) except for the ICF, which is signed by the subject and/or parent/guardian. The ICF will be kept separate from the other forms and documents.

5.3 SUBJECT DURATION

The study consists of a single visit. The visit will take approximately 30-45 minutes to complete, and subject participation is complete at the end. Subjects will be provided with the Investigator's contact information and instructed to notify the Investigator if they experience any complications from specimen collection procedures.

Subjects are free to withdraw consent and discontinue participation in the study at any time. A subject's participation in the study may be discontinued at any time at the discretion of the study staff. The following may be justifiable reasons for the study staff to remove a subject from the study:

1. The subject was erroneously included in the study or was found to have an exclusion criterion.
2. The subject is uncooperative or unable to complete the required study tasks
3. The subject experiences an Adverse Event (AE)/Serious Adverse Event (SAE) during the specimen collection procedure that is considered intolerable by subject or Investigator.

To the extent possible, safety data will be collected on subjects who discontinue participation in the study due to safety reasons.

6 STUDY POPULATION

6.1 INCLUSION CRITERIA

1. Individuals aged 14 years and older (self-collected) or individuals less than 14 years old but ≥ 2 years old (collected by an adult)
2. Human subjects suspected of respiratory viral infection consistent with COVID-19 or Influenza by their healthcare provider within 4 days of symptom onset
3. Must be willing to try Lucira COVID-19 & Flu test with an anterior nasal (nasal) swab specimen collected from both nostrils
4. Subject information shall include: gender, age, collection date, collection time, race, ethnicity, temperature, signs/symptoms, date of symptom onset, symptom severity, vaccination status, household income, education status, employment status, routine test data (results, methodology, date of collection, if available)

090177e19dd636e3\Approved\Approved On: 25-Jun-2023 03:44 (GMT)

6.2 EXCLUSION CRITERIA

1. Currently suffering from nasal trauma such as a nosebleed
2. Received a nasal rinse/wash/aspirates for standard of care testing
3. The subject is undergoing treatment for COVID-19 or Flu currently and/or within the past 14 days of the study visit, including but not limited to: inhaled influenza vaccine (FluMist®) or flu antiviral medication, which may include but is not limited to Amantadine (Symmetrel®), Rimantadine (Flumadine®), Zanamivir (Relenza®), Oseltamivir (Tamiflu®), or Baloxavir marboxil (Xofluza®).
4. The subject is currently receiving or has received within the past 30 days of the study visit an experimental biologic, drug, or device including either treatment or therapy.
5. The subject has previously participated in this research study
6. Incorrect comparator swab type or transport media
7. Incorrect specimen handling
8. Subjects not consented

6.3 SUBJECT COMPLETION, DISCONTINUATION AND WITHDRAWAL**6.3.1 SUBJECT COMPLETION**

Subject's participation is complete after sampling procedures. Subjects will be provided with the Investigator's contact information and will be instructed to notify the Investigator if they experience any complications from the specimen collection procedures.

6.3.2 SUBJECT DISCONTINUATION AND WITHDRAWAL

Subjects are free to withdraw consent and discontinue participation in the study at any time. A subject's participation in the study may also be discontinued at any time at the discretion of the Principal Investigator. The following may be justifiable reasons for the Investigator to remove a subject from the study:

- The subject was erroneously included in the study or was found to have an exclusion criterion.
- The subject is uncooperative (i.e., not providing swabs specimens for this research).
- The subject experiences an Adverse Event (AE)/Serious Adverse Event (SAE) during the specimen collection procedure that is considered intolerable by subject or Investigator.

If a subject decides to discontinue participation in the study, information about the reason(s) for discontinuation and recording of any potential AEs should be documented. The Investigator will provide information describing the reason for discontinuation. The Investigator will attempt to follow all AEs until resolution.

7 STUDY ASSESSMENTS AND PROCEDURES**7.1 MATERIALS****7.1.1 MATERIALS PROVIDED BY SPONSOR**

- Lucira COVID-19 & Flu Test which includes: 2 AA batteries, Test Unit, Sample Vial, Nasal Swab, and Quick Reference Instruction (QRI)
- Reference Swab Collection Kit including: Nasal swab, 3ml VTM, and biohazard collection bag with absorbent sheet
- Refrigerated shipping containers and shipping supplies
- Case Report Forms (CRF)

090177e19ddd636e3Approved\Approved On: 25-Jun-2023 03:44 (GMT)

Test kits will be provided by the Sponsor and a Test Kit provided to each subject by the Investigator. The Investigator or designee is responsible for maintaining accountability records for all inventory transactions (i.e., receipt, utilization, and return). The investigational product may only be used in accordance with this approved protocol and must not be used for any other purpose. Investigational product may only be used for subjects who have provided written informed consent to participate in this study and meet all inclusion/exclusion criteria.

An Investigational Product Accountability Log details the quantity of the device, the shipment of investigational material, and clinical supplies from the Sponsor or its representative to the Investigator. The Investigator must ensure that the investigational product is maintained at the prescribed environmental conditions in a controlled location with limited access, as directed in the Study Operations Manual.

The Investigator or designee must complete an Accountability Log upon completion or termination of the study. All unused study materials, after device accountability, together with a copy of the Accountability Form, will be returned to the Sponsor or its representative. A copy of all Accountability forms should be retained in the site files.

7.2 SCREENING AND ENROLLMENT

7.2.1 IDENTIFY POTENTIAL SUBJECTS

The potential subject will be asked to provide relevant medical history information regarding COVID-19 and Influenza, which will be evaluated against all inclusion and exclusion criteria. At the time of the study visit, the subject must be suspected of respiratory viral infection consistent with COVID-19 or Influenza by a healthcare provider. To be eligible for this study, subject must also be willing to try the Lucira COVID-19 & Flu test with an anterior nasal (nasal) swab specimen collected from both nostrils. Preliminary assessment of the subject by the Investigator/designee should be suggestive of COVID-19 or Influenza based upon his/her medical judgment.

7.2.2 OBTAIN WRITTEN INFORMED CONSENT

All potential study participants must be given time to review the consent form, have their questions answered to their satisfaction, and complete the IRB-approved informed consent prior to performing any study procedures. The informed consent process will be recorded on the source document to confirm that no study procedures were performed prior to obtaining the subject's consent/assent. Subjects will be given a copy of the informed consent form.

7.2.3 REVIEW INCLUSION/EXCLUSION CRITERIA

The Investigator and/or designee should review all criteria to determine if the subject is eligible for enrollment. Eligibility will be documented in the source document and CRF.

7.2.4 PRIOR AND CONCOMITANT MEDICATIONS AND THERAPIES

No subject should be denied necessary treatment because of being a participant in this study.

7.2.5 RECORD DEMOGRAPHICS, BASELINE CHARACTERISTICS, AND MEDICAL HISTORY

Data shall be documented and recorded during initial study visit.

090177e19dd636e3\Approved\Approved On: 25-Jun-2023 03:44 (GMT)

7.3 PROCEDURE

The Lucira COVID-19 & Flu Test shall be performed before reference test specimen collection at the clinical site. A study staff member will provide each subject with a Lucira COVID-19 & Flu Test Unit. Participants performing the self-collection or assisted collection will be asked to read the Quick Reference Instructions (QRI).

Participants shall be instructed to begin the Lucira test on their own according to the QRI. This will involve a nasal self-collection and running the test. The study staff shall document all observations during the subject collection. The study staff shall interpret the test result and document the results on the source documentation.

While the Lucira COVID-19 Test is running, the reference nasal swab shall be collected by the study staff. The study staff shall document collection details and ship samples to reference laboratory.

7.3.1 QUALITY CONTROL PROCEDURES

The Lucira COVID-19 & Flu Test does not require an external control be performed.

7.3.2 TESTING PROCEDURE

- **Sample Collection and Specimen Testing**

The Lucira nasal swab shall be obtained before the reference test sample is collected. Subjects will be provided with the Lucira COVID-19 & Flu Test and collect one (1) nasal swab according to the QRI. The participant shall test the sample on the Lucira COVID-19 & Flu Test. HCP shall observe the participant during this process and document any observations or deviations from the QRI.

If a swab is contaminated or the test is invalid, participants will be asked to collect a new sample and test the sample on a new device. The date and time of collection shall be documented. Contaminated swabs (e.g., dropped) should be discarded. One additional attempt shall be made to collect a clean swab.

- **Reference Nasal Swab (NS) Collection**

One NS for reference testing shall be obtained from each subject who completes the collection step specified in the QRI and runs the Lucira COVID-19 & Flu Test regardless of result. The reference collection is collected by the study staff.

If a swab is contaminated or the test is invalid, subjects will be asked to collect a new sample and test the sample on a new device. The date and time of collection will be documented. Contaminated swabs (e.g., dropped) should be discarded. One additional attempt may be made to collect a clean swab.

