1.1 SYNOPSIS

[figure not shown]
Protocol Title	Performance Evaluation of the Lucira COVID-19 & Flu Test as Compared to FDA cleared/authorized SARS-CoV-2 and Influenza A&B Assays
Protocol Number	09A-CLI-001
Objective(s)	The primary objective is to evaluate the performance of the Lucira COVID-19 & Flu Test as compared to FDA cleared or authorized SARS-CoV-2 and Influenza A&B Assays.
Number of Subjects	Minimum of 1000 Symptomatic subjects
Number of Sites	Minimum of 3 sites from at least 2 geographically diverse locations
Study Duration	At least 12 weeks

090177e19dd636e3\Approved\Approved On: 25-Jun-2023 03:44 (GMT)

Study Design	
This study is a prospective, multi-center study to evaluate the performance of the Lucira COVID-19 & Flu Test, a real-time RT-LAMP test intended for the qualitative detection and differentiation of RNA from SARS-CoV-2, Influenza A and Influenza B in self-collected nasal swab samples designed to report rapid test results. The Lucira COVID-19 & Flu Test will be compared with a composite reference method for the detection and differentiation of COVID-19, influenza A and influenza B virus in nasal swabs from patients with signs and symptoms of COVID-19 and/or flu-like illnesses.
 
After determining subject eligibility and following the completion of the informed consent process, each subject will receive a unique study identification number.
 
A subject's participation in this study will consist of one study visit. The subject self-collects a nasal swab sample according to Lucira COVID-19 & Flu Test instructions and runs test according to Quick Reference Instruction (QRI).
 
Following the Lucira COVID-19 & Flu Test self-collection will be an additional swab collection for reference method testing. One (1) additional NS specimen will be collected by the health care professional, prepared in Transport Medium, and sent to the reference laboratory as directed by the Study Operations Manual.
 
Each collection component (investigational product and reference method) may have a maximum of two swabs, including retests, for a maximum of four swabs per visit.

Study Population	
Subject demographics including gender, age, education level, employment status, and household income shall be collected.

090177e19dd636e3\Approved\Approved On: 25-Jun-2023 03:44 (GMT)

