5 STUDY DESIGN

5.1 STUDY DESIGN

The study is a prospective with a minimum of three (3) sites in the U.S. will participate in the study. The Investigational device shall be tested on-site, and the reference samples shall be sent a reference laboratory in the U.S. Testing in the reference laboratory will be performed by trained laboratory personnel. This investigational device testing is to be performed in a simulated-home environment with medical staff on site and shall include nasal swabs self-collected by study subjects per the QRI.

A qualified research person will be designated as the Investigator at each site, with the responsibility for oversight of the study in accordance with Good Clinical Practice (GCP) and regulatory requirements. The protocol and subject informed consent will be reviewed by an Institutional Review Board (IRB) and written IRB approval will be issued prior to enrollment of subjects into the study at that site.

A subject's participation in this study will consist of a single visit. Following completion of the informed consent process and a review of Inclusion/Exclusion criteria to determine eligibility, each subject will receive a unique study identification number.

Subjects will then be asked relevant medical history questions, including inquiries regarding the presence or absence of COVID-19 and influenza signs and symptoms, vaccine status and current medications taken. Subject demographics including age, sex, race, and ethnicity should also be collected at this time.

Two (2) swabs should be collected for this study: One (1) nasal swab for the Lucira COVID-19 & Flu Test and one (1) nasal swab for composite reference testing. The Lucira COVID-19 & Flu Test study swabs will be collected as directed in the Lucira COVID-19 & Flu Test Quick Reference Instruction (QRI). The reference method swab collection shall be collected by the HCP and prepared in Transport Medium. Each collection may have a maximum of two swabs, including retests, for a maximum of four swabs per visit. Swab specimens required for standard of care testing should be collected prior to the specimens collected for this investigation.

Subject shall be observed during the swabbing collection by the HCP and HCP shall document collection details and any collection issues. Nasal swabs obtained from self-collection will be discarded after having been used for testing per QRI. HCP to interpret and document results.

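### Does the re-collection sentence for the reference swab in 7.3.2 leave a failed reference test without a workable rule?

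*Combined protocol and SAP*

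**What the plan says.** Section 7.3.2 has two parallel bullets, one for the Lucira swab and one for the reference swab. The reference bullet first states: "The reference collection is collected by the study staff". Its next paragraph covers contaminated swabs and adds that where "the test is invalid, subjects will be asked to collect a new sample and test the sample on a new device", and it closes by allowing one further, optional attempt at a clean swab. The Lucira bullet contains nearly the same sentence, with participants in place of subjects.

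The other sections are consistent with each other:

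- **Who collects.** Section 5.1: "The reference method swab collection shall be collected by the HCP and prepared in Transport Medium". Section 7.3: "While the Lucira COVID-19 Test is running, the reference nasal swab shall be collected by the study staff". Section 9.1.4.1 also gives the task to a qualified professional.
- **Who tests.** Section 5.1: "Testing in the reference laboratory will be performed by trained laboratory personnel".
- **What the reference kit holds.** Section 7.1.1: "Reference Swab Collection Kit including: Nasal swab, 3ml VTM, and biohazard collection bag with absorbent sheet". It contains no test unit.
- **When.** Section 5.3: "The visit will take approximately 30-45 minutes to complete, and subject participation is complete at the end". Section 7.3.5 has specimens shipped within 24 hours, with aliquots stored for later testing.
- **How many swabs.** In section 1.1, each component ("investigational product and reference method) may have a maximum of two swabs, including retests, for a maximum of four swabs per visit").

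Section 8.3 defines one analysis set, which requires both a valid Lucira result and a valid reference result. It removes subjects with missing results and rules out imputation. Its retest rule and its invalid rates concern the Lucira test only.

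**The concern.** Taken at face value, the sentence gives the wrong person, the wrong instrument and the wrong time. Subjects do not collect the reference swab. The only device a subject could run is a Lucira unit. A laboratory result would normally be known only after the subject has gone home, although the synopsis counts reference retests among the swabs of one visit.

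If a site followed the sentence and the second Lucira result were then entered as the reference, the device would be compared with itself. If the sentence is set aside, section 8.3 offers no rerun step for an invalid reference, and no reference-invalid rate is planned.

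Positive and negative percent agreement are the performance endpoints, and a valid reference result decides who is counted. With targets of only 50 Flu A and 30 Flu B positives (section 8.1), undocumented or selective losses could matter near the 90% threshold of section 4.

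**Working it through.** The plan states no figure on this point, so there is nothing to reproduce. The check compares the sections and then gauges the size.

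**1. Could a Lucira repeat become the reference?** Section 5.1 defines the reference as laboratory testing on FDA cleared or authorized assays, and section 9.1.4.2 gives that testing to the reference site. Section 8.3 says that a valid result from a repeated Lucira test is reported as the Lucira result. A second run on a Lucira unit is therefore a Lucira result. No section makes it a reference result.

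**2. What does the sentence most plausibly mean?** By section 7.3 the reference swab is taken while the Lucira test is running, so a Lucira invalid would appear during or after that step. Reading the test and the new device as Lucira removes the conflicts over instrument and timing. What remains is who replaces a contaminated reference swab. The sentence before the paragraph assigns reference collection to staff, and the closing allowance of one more attempt names no other collector.

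**3. What happens to an invalid laboratory result?** It does not meet section 8.3's requirement of a valid reference result and is not imputed, so the subject is excluded if it stays unresolved. Section 9.1.8 requires deviations and incidents that lead to data exclusion to appear in the final report. The stored aliquots of section 7.3.5 make a laboratory rerun feasible, but the plan does not say whether one is done.

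**4. Size if invalid references are excluded.** The invalid rate r is an assumption: 1%, 3% or 5%. The positives n are the section 8.1 targets. Expected loss = n × r.

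| Target | r = 1% | r = 3% | r = 5% |
|---|---|---|---|
| COVID-19, n = 120 | 1.2 | 3.6 | 6.0 |
| Flu A, n = 50 | 0.5 | 1.5 | 2.5 |
| Flu B, n = 30 | 0.3 | 0.9 | 1.5 |

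These losses treat the targets as a fixed pool. Section 8.1 instead ties recruitment to reaching at least 1000 negatives, and section 9.1.5 has enrollment monitored. If a subject without a valid reference counts toward neither group, enrollment can run slightly longer. At r = 5%, 30/(1 − 0.05) = 31.6, so 32 Flu B positives would be needed to keep 30.

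**5. Effect on the estimate.** With a agreeing and c disagreeing positives, and invalids unrelated to the Lucira result, expected counts give PPA = a(1 − r)/[(a + c)(1 − r)] = a/(a + c), which is unchanged.

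**6. Effect on precision.** The Wilson 95% limits are [p + z²/(2n) ± z√(p(1 − p)/n + z²/(4n²))]/(1 + z²/n), with z = 1.96. For Flu B, 27/30 = 90.0% gives 74.4% to 96.5%. Losing one agreeing positive, 26/29 = 89.7% gives 73.6% to 96.4%. The lower limit moves by 74.4 − 73.6 = 0.8 points.

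**The case for a change.** The strongest case for a change is that the sentence is operative text for sites. Calling it a slip does not supply the missing rule, because striking it leaves no stated rerun procedure. The two-swab limit is a cap and not a procedure. The extra testing in section 7.3.5 is tied to discrepant results, not to invalid ones. A choice between rerun and exclusion made once Lucira results are known could favor the device. Dropping two disagreeing Flu A positives would turn 44/50 = 88.0% into 44/48 = 91.7%, which crosses the 90% threshold. The remedy would cost a few sentences.

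Part of this stands. The wording is wrong for a reference swab, and the rerun step is not stated. The reporting in section 9.1.8 is also less detailed than a count by virus would be.

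The harm does not follow. The 44/50 example needs two losses that both fall on disagreeing positives, and nothing in the plan would steer invalid results toward them. A rerun followed by exclusion and exclusion at once both keep the comparison with the laboratory assay intact. They differ only in how many subjects are retained. The laboratory, or the Study Operations Manual mentioned in sections 1.1 and 7.1.1 and not available here, can settle a repeat run without altering the endpoint.

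**Conclusion.** No change to the plan is needed. The contradiction in section 7.3.2 is a clerical carry-over whose correct reading is clear from the neighboring text: staff take any replacement reference swab, and the laboratory runs it. The unstated rerun step is a gap that analysts and the laboratory would fill sensibly, within the requirement of section 8.3 for a valid reference result.

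The expected effect on agreement is nil if invalid references are unrelated to the Lucira result. The loss of precision is small: at an assumed 5% invalid rate, about 1.5 of 30 Flu B positives if they are not replaced by further enrollment. The conclusion rests on that independence and on assumed invalid rates of 1% to 5%, since the documents give none. It also rests on the inference, from the short visit and the shipping to an off-site laboratory, that reference results arrive after the subject has left.

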7.3.3 COMPENSATION

Subjects will be compensated for their visit time and inconvenience. Subjects who are disqualified during the study or are unable to complete the research through no fault of their own may still receive compensation. Compensation may be provided in the form of a Gift card. Proper handling of compensation shall require sites to document individual subject compensation in the associated source documents, followed by tracking in the site Compensation log.

